4.2. Treatment Arms and Duration

The total duration of subject involvement is up to 16 weeks (Screening to Follow-up) as described below:

- Screening: Screening will occur at least one week prior to but not more than 30 days prior to washout.
- ESA Washout: Subjects that meet eligibility criteria will begin the 2-week ESA washout at Week -2.
 - This should be timed such that this day occurs on the date that would have been the next scheduled dose of ESA (or as close as practicable).
 - For subjects with a three-times weekly dialysis schedule, this day must not occur on the first dialysis session of the week (e.g., if Monday-Wednesday-Friday schedule, the study visit cannot be on Monday).
 - For subjects with a four- to five-times weekly dialysis schedule, this day can be on any hemodialysis session of the week.
- Randomization & Acute Challenge 1 (Day 1): Subjects will be randomized 1:1 to two treatment arms as described in [Table 1](#) and will begin a 24-hr Acute Challenge where the acute BP effects of daprodustat and epoetin alfa will be

evaluated. This challenge will be initiated promptly following the subject's dialysis session.

- **Hgb Maintenance Period:** Subjects randomized to daprodustat will start an 8-week Hgb maintenance period based on a starting dose and dose adjustment algorithm as described in Section 6.4.1. Subjects randomized to epoetin alfa will begin an 8-week Hgb maintenance period where Hgb will be managed in accordance with local labelling.
- **Acute Challenge 2:** At the end of the 8-week Hgb maintenance period, subjects will repeat the procedures of Acute Challenge 1 utilizing the same treatment administered in Acute Challenge 1. This challenge will be initiated promptly following the subject's dialysis session.
- **Follow-up:** A Follow-up visit will be scheduled to occur 14 ± 3 days after completing treatment.

Table 1 Treatment Arm Descriptions

Treatment Arm	Acute Challenge 1	Hgb Maintenance Phase	Acute Challenge 2
A	100 U/kg IV epoetin alfa	IV epoetin alfa according to label	100 U/kg IV epoetin alfa
B	24 mg daprodustat	QD daprodustat according to dose adjustment algorithm (Section 6.4.1)	24 mg daprodustat

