¹No change is defined as an increase < 0.5 g/dL

²Increase is defined as an increase ≥ 0.5 g/dL

³ If Hgb remains ≥12.0 at next visit, the subject should be withdrawn from the study. If the Hgb drops below 12.0, the subject should be restarted on the next lowest dose.

⁴ Only applies at Day 57 if a repeat AC2 is necessary. The dose should be decreased for the 1 week between AC2 and Additional AC2.

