6.7. Compliance with Study Treatment Administration

For subjects randomized to daprodustat, treatment dosing details including dates for dose increases/reductions, will be recorded in RAMOS NG.

For subjects randomized to daprodustat, for Acute Challenge 1 and 2, study site personnel will confirm compliance. When daprodustat is administered at home (Hgb maintenance period), subjects will be instructed to return all unused randomized treatment at each clinic visit. A record of the number of daprodustat tablets dispensed to and taken by each subject will be maintained and reconciled with randomized treatment and compliance records.

For subjects randomized to epoetin alfa, they will receive all study treatment directly from the investigator or designee, under medical supervision. The date and time of each dose administered in the clinic will be recorded in the source documents. The dose of study treatment and study subject identification will be confirmed at the time of dosing by a member of the study site staff other than the person administering the study treatment.

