**CONFIDENTIAL**

205665

A listing of which participants reported specific adverse events will be produced.

The hierarchical relationship between MedDRA SOCs, PTs and verbatim text will be listed for all adverse events.

Adverse events occurring during the 24-hour acute challenge will be grouped in the appropriate acute challenge phase. Any AE occurring after AC2 but before repeat-AC2 will be grouped in the HGB maintenance phase.

Adverse events occurring after the last on treatment date will be grouped either in early withdrawal or follow-up depending on the final status of the subject,

*Serious and Other Significant Adverse Events*

The number and percentage of participants and the number of occurrences of SAEs will be provided for each treatment group. These events will be summarized by treatment group, primary system organ class, and preferred term. Pre-treatment, post-randomization, treatment emergent and follow-up SAEs will be summarized separately. Treatment emergent SAE preferred terms will also be summarized by treatment group and overall frequency.

A listing of reasons for considering as a SAE will be produced for all treatment emergent SAEs.

The number and percentage of participants and the number of occurrences of treatment emergent drug-related SAEs, and drug-related fatal SAEs will be summarized by treatment group.

A listing of treatment emergent fatal SAE records and a listing of treatment emergent non-fatal SAE records will be provided.

The number and percentage of participants reporting treatment emergent AEs leading to discontinuation of randomized treatment will be summarized by treatment group, primary system organ class, and preferred term.

A listing of treatment emergent AEs leading to discontinuation of randomized treatment will be provided.

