**14.4.2. Treatment Emergent Flag for Adverse Events**

All AEs (non-serious AEs and serious AEs) will be collected and recorded on the eCRF from the start of treatment, including washout period, until the follow-up visit at the time points specified in the SoA from [Appendix 2](#). Serious AEs assessed as related to study participation (e.g., study treatment, protocol-mandated procedures, invasive tests, or change in existing therapy) or related to a GSK product will be recorded on the eCRF from the time a participant consents to participate in the study up to and including any follow-up contact.

Treatment State	Definition
Pre-treatment	
 
For participants with a non-missing screen failure date, if AE onset is on or before the screen failure date: AE Start Date <math>\leq</math> Screen Failure Date
 
For randomized participants with a missing treatment start date, all AEs are considered pre-treatment
 
For randomized subjects with a non-missing treatment start date, if AE onset date is before treatment start date: AE Start Date <math><</math> Treatment Start Date
 

Post-randomization	If AE onset date or AE worsening date is on or after the randomization date Randomization date $\leq$ AE Start Date Randomization date $\leq$ AE Worsening Date
Treatment emergent	If AE onset date or AE worsening date is on or after treatment start date & on or before the last non-zero dose date plus 1 day. Treatment Start Date $\leq$ AE Start Date $\leq$ Last Non-Zero Dose Date + 1 day Treatment Start Date $\leq$ AE Worsening Date $\leq$ Last Non-Zero Dose Date + 1 day
Follow-up	If AE onset date or AE worsening date is after the last non-zero dose date plus 1 day. AE Start Date $>$ Last Non-Zero Dose Date + 1 day AE Worsening Date $>$ Last Non-Zero Dose Date + 1 day
Onset /Worsening Time Since 1 st Dose (Days)	If Treatment Start Date $>$ AE Onset Date = AE Onset Date - Treatment Start Date + 1 If Treatment Start Date $\leq$ AE Onset Date = AE Onset Date - Treatment Start Date + 1 If Treatment Start Date $>$ AE Worsening Date = AE Worsening Date - Treatment Start Date If Treatment Start Date $\leq$ AE Worsening Date = AE Worsening Date - Treatment Start Date + 1 Missing otherwise.

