**NOTES:**

- AEs that occur or worsen during interruptions of randomized study treatment will be classified as treatment emergent and post-randomization.
- If the treatment stop date is missing and the treatment start date is non-missing and the AE onset date or AE worsening date is on or after the treatment start date, then the AE will be considered to be treatment emergent.
- If AE onset date or AE worsening date is missing and AE resolution date is before the treatment start date, then the AE will be classified as Pre-treatment.
- If AE onset date or AE worsening date is missing and AE resolution date is either missing or on or after treatment start date, then the AE will be classified as treatment emergent and post-randomization.

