**CONFIDENTIAL**

205665

Time Definitions (per GSK standard principles)

 
• 1 week = 7 days
 
• 1 month = 30.4375 days
 
• 1 year = 365.25 days
 

Last Non-Zero Dose Date

 
• Date of last actual dose of randomized study treatment from the IP Discontinuation eCRF form. 
 
○ The dose steps used by the dosing algorithm described in the protocol include a dose hold or a zero dose. If participants are assigned by the algorithm to a zero dose, they do not receive randomized treatment for that period. Hence, it would be possible for a participant to complete the study, while still following the dosing algorithm, but not actually taking any actual randomized treatment. The last non-zero dose date then captures the latest date in the study that a participant physically took a dose of randomized treatment.
 
 
 
• The eCRF allows for the possibility of partial or missing dates to be recorded for the last actual dose of randomized study treatment on the IP Discontinuation form (i.e., missing day, or day and month, or day and month and year). In such a case, or in case of a missing IP Discontinuation form, the following conventions will be applied in order to impute a last non-zero dose date: 
 
○ Missing day: 
 
▪ The last day of the month will be used, unless the treatment stop date also occurs in the same month; in this case, the treatment stop date will be used.
 
 
 
○ Missing day and month; 
 
▪ '31' will be used for the day and 'Dec' will be used for the month, unless the treatment stop date also occurs in the same year; in this case the treatment stop date will be used.
 
 
 
○ Missing day, month, and year:
 
 
 
• Treatment stop date will be used only for participants who have a non-missing treatment start date.
 

Screening and Washout visits
Screening

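### A cutoff of last dose plus one day fits daily daprodustat but not intermittent IV epoetin, so displays limited to treatment-emergent events can count treatment-ending events unequally

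*SAP*

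**What the plan says.** SAP 14.4.2 gives one rule for both arms. Treatment-emergent status requires onset or worsening from the treatment start date and "on or before the last non-zero dose date plus 1 day"; anything later is Follow-up. SAP 14.6.1 fixes the anchor: "The last non-zero dose date then captures the latest date in the study that a participant physically took a dose of randomized treatment". A zero dose assigned by the algorithm does not move it. A note to 14.4.2 adds: "AEs that occur or worsen during interruptions of randomized study treatment will be classified as treatment emergent and post-randomization".

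The dosing patterns differ by arm. Protocol 4.2 has "QD daprodustat according to dose adjustment algorithm" in one arm and IV epoetin according to label in the other. Protocol 6.7 says of epoetin subjects that "they will receive all study treatment directly from the investigator or designee, under medical supervision". No epoetin interval is stated. Inclusion criterion 3 requires dialysis three to five times a week.

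Displays that use the flag:
- Appendix 12 limits Tables 2.3-2.9 (common, drug-related and common non-serious AEs) to treatment-emergent events.
- SAP 8.1 says "The number and percentage of participants reporting treatment emergent AEs leading to discontinuation of randomized treatment will be summarized by treatment group", and "A listing of treatment emergent fatal SAE records and a listing of treatment emergent non-fatal SAE records will be provided".
- In Appendix 12, Table 2.13 and Listings 17-20, which cover the same ground, carry no such limit.

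SAP 8.1 and 8.2 also plan post-randomization and follow-up summaries of AEs, SAEs and AESIs.

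**The concern.** A one-day tail is as long as the gap between daily tablets. It is shorter than the gap between intermittent clinic injections. When an event itself stops treatment, it also fixes the last dose date. Protocol 5.5.1 makes myocardial infarction and stroke mandatory reasons to stop, so this is a foreseeable case. Suppose a stroke occurs two days after the most recent epoetin dose and no further dose is given: it is Follow-up. A daprodustat subject with a stroke on the same calendar day would normally have dosed that day or the day before, so it is treatment-emergent.

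At stake is whether the treatment-emergent-only displays can be compared between arms for early discontinuers, and whether an AE can cause discontinuation yet be absent from the summary of AEs leading to discontinuation.

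**Working it through.** **Size of the group.** Protocol 9.2.1 plans 31 randomized per arm with 20% withdrawal: 31 × 0.80 = 24.8, which reproduces the stated 25 at Acute Challenge 2. Early withdrawals are 31 × 0.20 = 6.2 per arm. Subjects who complete Acute Challenge 2, or its repeat, take their last dose at that challenge in both arms, so their windows match.

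**Share of onset days outside the window.** Let *g* be a gap in days between doses, with onset equally likely on any day. Days 0 and +1 after the last dose count.
- Variant A, an event on a dosing day follows that day's dose: lags run 0 to *g* − 1, and max(0, *g* − 2) days fall outside.
- Variant B, an event on a dosing day precedes and prevents the dose: lags run 1 to *g*, and max(0, *g* − 1) days fall outside.

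Sum over the gaps and divide by the total days. All epoetin rows are assumptions.

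| Schedule | Gaps (days) | A | B |
|---|---|---|---|
| Daprodustat, daily | 1 × 7 | 0/7 | 0/7 |
| Epoetin, five times weekly | 1, 1, 1, 1, 3 | 1/7 (14%) | 2/7 (29%) |
| Epoetin, three times weekly | 2, 2, 3 | 0+0+1 = 1/7 (14%) | 1+1+2 = 4/7 (57%) |
| Epoetin, weekly | 7 | 5/7 (71%) | 6/7 (86%) |
| Epoetin, every two weeks | 14 | 12/14 (86%) | 13/14 (93%) |

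Under either variant, the share falls to zero once the window equals the longest gap: +3 days for the 2-2-3 pattern, +7 for weekly, +14 for every two weeks.

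**Ceiling on events moved.** If every early epoetin withdrawal were caused by an AE, the expected number reclassified would be 6.2 × 1/7 = 0.9 to 6.2 × 4/7 = 3.5 for three-times-weekly dosing, and 6.2 × 5/7 = 4.4 to 6.2 × 6/7 = 5.3 for weekly. Some withdrawals will have other causes, so the true figure is lower. One subject is 1/31 = 3.2%, above the unrounded 2% threshold for the common-AE tables, so a single reclassification can put a preferred term in or out.

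**Holds that end in withdrawal.** Protocol 6.4.1 sets a two-week hold at a confirmed Hgb of 12.0 or more, and "If Hgb remains ≥12.0 at next visit, the subject should be withdrawn from the study". Protocol 5.5.1.1 and 7.5.1.1 set a one-week hold at Day 57, also with possible withdrawal.
- Under the 14.4.2 definition with the 14.6.1 anchor, a two-week hold has 13 of 14 days outside the window if the last dose was on the visit day, or 14 of 14 if it was the day before. A one-week hold has 6 or 7 of 7.
- Under the note on interruptions, the count outside is 0.

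The SAP does not say which prevails when dosing never resumes.

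**The case against.** The strongest reply is that nothing disappears. AEs, SAEs and AESIs are also tabulated post-randomization, where the dosing interval has no effect, and death, myocardial infarction, stroke and thrombosis are AESIs. This stands. A reader might infer that the comparison of the most serious events is biased throughout; the documents do not support that, because those summaries count both arms alike.

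Second, a reader might infer that events during a high-Hgb hold that ends in withdrawal are excluded. The note on interruptions sets no condition that dosing resume. It would add little if it did, since a resumed dose already moves the anchor past the hold. This also stands: the fault is an unresolved conflict, not a settled exclusion.

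Third, a reader might infer that AEs leading to discontinuation will be missing from Table 2.13. Only the text of SAP 8.1 imposes that limit; Appendix 12 does not. That is a mismatch to reconcile.

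Fourth, the epoetin interval is not in the documents, few subjects are affected, and the safety objective concerns daprodustat rather than a between-arm test. These limit the size but do not remove the point. Even five-times-weekly dosing leaves a gap longer than the window, and the tables are laid out by treatment group.

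**Conclusion.** The point holds in a limited form and should be corrected. One cutoff applied to two dosing patterns gives unequal capture in Tables 2.3-2.9 and, on the text of SAP 8.1, in the discontinuation summary and the fatal and non-fatal SAE listings. It affects only subjects who stop before Acute Challenge 2, about 6 per arm. The size depends on an assumed epoetin interval and on onset being spread evenly over days.

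A reader might also infer a net bias in favour of epoetin. The documents do not support a direction. The dosing gap removes epoetin events, but the two-week hold is written only into the daprodustat algorithm, so excluding those days would remove daprodustat events. The Day 57 hold applies to both arms.

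**What to change.** 1. Base the between-arm displays in Tables 2.3-2.9 and 2.13 and Listings 17-20 on the post-randomization flag that 14.4.2 already derives, or on one common window at least as long as the longest dosing interval. Keep the +1 day set as a supplementary display.
2. State in 14.4.2 that the note on interruptions governs the classification of AEs during a hold, whether or not dosing resumes.
3. Reconcile SAP 8.1 with Table 2.13 and Listings 17-20, so that every AE leading to discontinuation appears in the discontinuation table.

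The cost is SAP wording and re-running displays on data already collected, since Protocol 7.3.1.1 collects AEs to the follow-up contact. The downside is that some events after treatment ends enter the main tables. These include events after any anemia therapy restarted before the follow-up visit, which Protocol 4.1 allows when medically necessary. The supplementary +1 day display lets a reader see how much this matters.

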**CONFIDENTIAL**

205665

**NOTES:**

- AEs that occur or worsen during interruptions of randomized study treatment will be classified as treatment emergent and post-randomization.
- If the treatment stop date is missing and the treatment start date is non-missing and the AE onset date or AE worsening date is on or after the treatment start date, then the AE will be considered to be treatment emergent.
- If AE onset date or AE worsening date is missing and AE resolution date is before the treatment start date, then the AE will be classified as Pre-treatment.
- If AE onset date or AE worsening date is missing and AE resolution date is either missing or on or after treatment start date, then the AE will be classified as treatment emergent and post-randomization.

## 14.5. Appendix 5: Data Display Standards & Handling Conventions

### 14.5.1. Reporting Process

Software	

 
The currently supported versions of SAS software, Version 9.2 (or higher) will be used for all analyses unless otherwise specified. Additionally, R Version 3.1.0 or higher may be used for analysis and the production of graphics.
 
	
Reporting Area	
HARP Server	: us1salx00259
HARP Compound	: gsk1278863/mid205665
Analysis Datasets	

 
Analysis datasets will be created according to clinical data interchange standards consortium (CDISC) standards: study data tabulation model (SDTM) implementation guide (IG) Version 3.1.3 with some updates from Version 3.2, Analysis data model (ADaM) IG Version 1.1, and GSK ADaM specification template.
 
For creation of ADaM datasets (ADCM/ADAE), the same version of dictionary datasets will be implemented for conversion from system independent (SI) to SDTM.
 
	
Generation of RTF Files	

 
Rich text format (RTF) files will be generated for Tables.
 
	

### 14.5.2. Reporting Standards

General	

 
The current GSK Integrated Data Standards Library (IDSL) will be applied for reporting, unless otherwise stated (IDSL Standards Location: https://spope.gsk.com/sites/IDSLLibrary/SitePages/Home.aspx): 
 
4.03 to 4.23: General Principles
 
5.01 to 5.08: Principles Related to Data Listings
 
6.01 to 6.11: Principles Related to Summary Tables
 
7.01 to 7.13: Principles Related to Graphics
 
 
 
Do not include subject level listings in the main body of the GSK Clinical Study Report. All subject level listings should be located in the modular appendices as ICH or non-ICH listings
 
In all displays (TFLs) the term "Subjects" will be used to refer to the "Participants".
 
	
Formats	

 
GSK IDSL Statistical Principles (5.03 & 6.06.3) for decimal places (DP's) will be adopted for reporting of data based on the raw data collected, unless otherwise stated.
 
Numeric data will be reported at the precision collected on the eCRF.
 
The reported precision from non eCRF sources will follow the IDSL statistical principles but may be adjusted to a clinically interpretable number of DP's.
 
	
Planned and Actual Time	

 
Reporting for tables, figures and formal statistical analyses: 
 
Planned time relative to dosing will be used in figures, summaries, statistical analyses and calculation of any derived parameters, unless otherwise stated.
 
The impact of any major deviation from the planned assessment times and/or scheduled visit days on the analyses and interpretation of the results will be assessed as appropriate.
 
 
 
	

**CONFIDENTIAL**

205665

 
Reporting for Data Listings:           
 
Planned and actual time relative to study drug dosing will be shown in listings (Refer to IDSL Statistical Principle 5.05.1).
 
Unscheduled or unplanned readings will be presented within the subject's listings.
 
 
 
	
Unscheduled Visits	

 
Unscheduled visits will not be included in summary tables, with the following exceptions:           
 
If the table includes a row for all post-baseline assessments, unscheduled visits will be included in this row. All unscheduled visits will be included in listings.
 
 
 
	
Descriptive Summary Statistics	
Continuous Data	Refer to IDSL Statistical Principle 6.06.1
Categorical Data	N, n, frequency, %
Graphical Displays	

 
Refer to IDSL Statistical Principals 7.01 to 7.13.
 
	

**14.5.3. Reporting Standards for Pharmacokinetic**

Pharmacokinetic Concentration Data	
Descriptive Summary Statistics, Graphical Displays and Listings	
Refer to IDSL PK Display Standards. Refer to IDSL Statistical Principle 6.06.1. Note: Concentration values will be imputed as per GUI_51487 for descriptive summary statistics/analysis and summarized graphical displays only.

Pharmacokinetic Parameter Derivation	
Descriptive Summary Statistics. (Log e Transformed)	
N, n, geometric mean, 95% CI of geometric mean, standard deviation (SD) of log transformed data and %CVb will be reported.  <math>CV_b (\%) = \sqrt{(\exp(SD^2) - 1) * 100}</math>          [NOTE: SD = SD of loge transformed data]

Parameters Not Being Log e Transformed	%AUC ex and T max
Summary Tables	C max , T max , AUC(0-t), AUC (0-∞), t 1/2 , and %AUC ex as data permit. The following PK parameters will not be summarised: first point, last point, and number of points used in the determination of λ z .
Listings	Include PK Parameters C max , T max , AUC(0-t), AUC (0-∞), and t 1/2 as data permit. Include the first point, last point and number of points used in the determination of λ z .

CONFIDENTIAL

205665

## 14.6. Appendix 6: Derived and Transformed Data

### 14.6.1. General

Multiple Measurements at One Analysis Time Point

 
• Mean of the measurements will be calculated and used in any derivation of summary statistics but if listed, all data will be presented.
 
• If there are two values within a time window (as per Section 14.3.1) the value closest to the target day for that window will be used. If values are the same distance from the target, then the mean will be taken.
 
• Participants having both High and Low values for Normal Ranges at any post-baseline visit for safety parameters will be counted in both the High and Low categories of “Any visit post-baseline” row of related summary tables. This will also be applicable to relevant Potential Clinical Importance summary tables.
 

Treatment Day

 
• Calculated as the number of days from treatment start date: 
 
• Treatment Start Date = Missing → Treatment Day = Missing
 
• Ref Date < Treatment Start Date → Treatment Day = Ref Date – Treatment Start Date
 
• Ref Date ≥ Treatment Start Date → Treatment Day = Ref Date – (Treatment Start Date) + 1
 
 
 

Randomization Date

 
• Date subject was randomized
 

Study Day

 
• Calculated as the number of days from First Dose Date: 
 
• Ref Date = Missing → Study Day = Missing
 
• Ref Date < Randomization Date → Study Day = Ref Date – Randomization Date
 
• Ref Date ≥ Randomization Date → Study Day = Ref Date – (Randomization Date) + 1
 
 
 

Study Completion/Withdrawal Date

 
• Date of withdrawal for subjects withdrawing (i.e., subjects who actively withdraw or are deemed lost to follow-up) from study or date of completion of study for subjects who complete the study.
 
• Early withdrawal subjects during washout will be calculated if the subject has a withdrawal date but no randomization date
 

First Study Contact Date

 
• First study contact with the subject while on the study is defined as consent date 
 
○ If subject has been re-screened, latest consent date will be used
 
 
 

Last Study Contact Date

 
• Last study contact with subject (clinic, telephone or other contact with subject) with the subject while on the study
 

